## Part A.4. Questions Common to All Studies

*For all questions, if the study involves only secondary data analysis, focus on your proposed design, methods and procedures, and not those of the original study that produced the data you plan to use.*

**A.4.1. Brief Summary.** Provide a *brief* non-technical description of the study, which will be used in IRB documentation as a description of the study. Typical summaries are 50-100 words. *Please reply to each item below, retaining the subheading labels already in place, so that reviewers can readily identify the content.*

**Purpose:** Advanced age and common genetic polymorphism of the antioxidant enzyme glutathione-s-transferase M1 (GSTM1) appear to confer susceptibility to ambient particulate matter (PM). This study will compare responses to PM exposure in older volunteers with GSTM1 null and sufficient genotypes.

**Participants:** 30 healthy 50-75 yo subjects.

**Procedures (methods):** Subjects will be placed on a diet restricted of omega and oleic fatty acids for approximately 42 days prior to undergoing sequential exposures to air (control) and concentrated ambient PM (CAP) for 2 hr. Pulmonary, vascular and cardiac function will be evaluated pre, immediately post and 18 hr post exposure.

**A.4.2. Purpose and Rationale.** Provide a summary of the background information, state the research question(s), and tell why the study is needed. If a complete rationale and literature review are in an accompanying grant application or other type of proposal, only provide a brief summary here. If there is no proposal, provide a more extensive rationale and literature review, including references.

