## Subject Qualification

**Screening:** Subjects will be recruited by the Westat Corporation (see section B1 below). During an initial telephone interview, the subjects will receive information regarding the study and their eligibility status will be assessed. Subjects whose responses indicate that they are likely to meet the criteria will be scheduled for a genetic screening appointment in the medical station in the US EPA Human Studies Facility (HSF). Depending on the need to maintain a representative population of subjects over time, GSTM1 null or sufficient subjects may be enrolled exclusively at various points in the study. At that time a genotype screening informed consent form and a consent form for storing blood with identifying information will also be signed. The subjects identified from a previous study (see page 26, methods of recruiting) will not need genotype screening. Subjects will then undergo a brief medical history screening and blood pressure measurement. Subjects will then have approximately 20 ml of blood collected. A portion of the blood will be used for genetic screening for GSTM1 sufficiency and another portion of the blood will be used for the cholesterol levels, fatty acid analysis, and biochemistry analysis. Information obtained from the blood analyses at this point could be used by the study physicians to stop a subject's participation or end the study. Subjects will be given a copy of the Medical History Form to be filled out and mailed back after they are selected on the genotype.

**GSTM1/GSTP1 genotype screening:** A portion of the blood sample (about 5 ml) will be used for genotyping of GSTM1 and other non-selective genotypic markers such as GSTP1. Total DNA will be isolated from the blood sample and polymeric chain reaction (PCR) will be run to determine if the subject carries a GSTM1 positive or null gene polymorphism.

**Physical exam:** Subjects who are not excluded during the genetic screening will be scheduled for a physical examination in the HSF. During this visit, subjects will sign an informed consent to undergo the screening procedures and physical examination as per the previously UNC IRB-approved protocol, Recruitment and Screening of Potential Participants for U.S. EPA Studies (95-EPA-66). Subjects will then undergo a physical exam, pulse oximetry, and screening/baseline 12-lead electrocardiogram (ECG). A menstrual history will be collected on all female subjects.

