- **Brachial artery ultrasound.** Brachial artery ultrasound (BAU) to evaluate flow-mediated dilatation will be performed using a 14 MHz imaging probe interfaced with an Ultrasonix SP or Touch Pharma ultrasound machine. The diameter of the brachial artery will be measured at baseline, during reactive hyperemia and after administration of sublingual nitroglycerin. The subject will lie supine, and a pneumatic tourniquet will be placed around the right upper arm proximal to the target artery. Gated baseline images of the brachial artery will be acquired after 15 minutes of supine rest. The pneumatic cuff will then be inflated to a pressure of 200 mm Hg for 5 minutes, and increased flow will be induced by sudden cuff deflation. A second scan will be performed following deflation. The subject will rest another 10 minutes and a third ultrasound scan will be performed. Sublingual nitroglycerin (~0.4 mg) will be administered, followed in three to four minutes by the final ultrasound study. Subjects will then rest quietly for 5 minutes. Images of the brachial artery will be acquired and stored on a personal computer, and subsequently analyzed using a semi-automated offline quantification system.
- **Pulmonary function:** will be measured by spirometry, including measurement of single breath CO diffusing capacity ( $D_LCO$ ). Cardiac output ( $Q_c$  or pulmonary capillary flow) will be simultaneously measured from the uptake of inhaled acetylene gas during the same single breath procedure.
- **Blood sampling:** approximately 46.2 ml of blood will be collected pre-exposure in the study.

- *Symptom questionnaire* before and after exposure may be collected.
- **Blood Pressure Monitor:** An ambulatory blood pressure monitoring device will be placed on the subject's arm and begin collecting readings. Subjects will wear the blood pressure monitor and cuff for the rest of the day after leaving the facility but will be instructed to remove it before going to bed.

**Exposure:** All exposures will be carried out at the EPA Human Studies Facility on the UNC campus. Subjects will enter an exposure chamber for the 2-hour exposure to clean air. The next day they will undergo exposure to fine/ultrafine CAP for 2 hours. The CAP exposure day may be rescheduled if the particulate concentrations are too low on the scheduled day.

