The concentration of particles delivered to the chamber will vary depending on the levels of naturally occurring particles in the Chapel Hill air. Although 24 hr averages seldom exceed 15-20 ug/m^3, peak values in the summer can be as high as 50-60 ug/m^3 with lower values during the rest of the year. A face mask is used to reduce the daily and seasonal variability of PM concentration. Our past experience provides a basis to expect the particle mass delivered to the mask will be up to 600 ug/m^3. The particle burden, on a mass basis presented to the volunteer will not exceed an exposure an individual receives over a 24 hour period while visiting a typical urban center in America on a smoggy day. The particle mass of the outdoor air entering and exiting the aerosol concentrator will be monitored continuously. Filter samples will be obtained from the devices located upstream from the chamber and analyzed for both mass and chemical composition of particles. If it is confirmed that particulate mass levels exceed 600 ug/m^3 for greater than 6 minutes, exposure will be terminated. The process for confirmation may take up to

additional 10 minutes. The shutdown procedure involves venting a valve on the exposure chamber, which markedly reduces the particle exposure, and alerting the investigator with both auditory and visual signals leading to removal of the subject from the chamber. Blood pressure, telemetry, and oxygen saturation will be measured during the exposure period.

**Immediate Post-exposure:** Subjects will be released while wearing the Holter and blood pressure monitors. Symptoms questionnaire after exposure will be collected. Blood pressure, lung function, endothelial cell function, and heart rate variability will be measured and approximately 46.2 ml of blood samples will be collected.

**Eighteen Hours Post-PM exposure:** Eighteen hours after the exposure, the subjects will return to the HSF to undergo a brief medical evaluation, including blood pressure, spirometry (pulmonary function testing) and endothelial cell function (BAU) measurements. The subject will then be allowed to relax for 20-30 minutes in a reclined position, after which a 10-minute resting HRV measurement will be obtained, and approximately 46.2 ml of blood will be taken. Holter monitor will be removed.

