- **Confidentiality** Risk of breach of confidentiality is minimal. All subjects will be assigned a study number which will be used for data recording – not the subject’s name. The study number is all that will be entered into computer databases. All paper files that may contain the subject’s name or screening number are secure in the EPA building that has limited access 24 hours/day. Any abnormal medical findings (CBC, ECG, brachial artery ultrasound image, spirometry) will be discussed with the volunteer and the volunteer will be counseled to seek treatment from his/her personal physician if indicated. Samples will be stored at the U.S. EPA HSF. A numeric coding system will be used to ensure that subjects cannot be directly identified from the samples alone.

**A.4.8. Data analysis.** Tell how the qualitative and/or quantitative data will be analyzed. Explain how the sample size is sufficient to achieve the study aims. This might include a formal power calculation or explanation of why a small sample is sufficient (e.g., qualitative research, pilot studies).

To test our hypothesis that CAP causes adverse cardiovascular effects in GSTM1 null older human volunteers, we will measure a number of relevant endpoints, including blood pressure, HRV, brachial arterial blood flow rate, change in blood coagulation factors, platelets, fibrinogen, c-reactive protein, lactate, plasminogen activator inhibitor, ferritin, and  $\alpha$ 1-antitrypsin. In this study, our primary endpoints will be HRV measurement and peripheral venous blood markers. Our secondary endpoints will be endothelial cell function and pulmonary function measurements. Statistical data analyses will consist of ANOVA for continuous variables and rank sum tests for non-continuous variables pre- and post-exposure. A  $p$  value of 0.05 or less will be considered significant.

The sample size was calculated to detect a difference of 10% change in HRV assuming a standard deviation of 9%. Using GraphPad software, an N of 15 was derived using a power of 0.8 and an  $\alpha$  of 0.05. This study will enroll approximately 30 subjects in order to provide sufficient power to all for the examination of differences between GSTM1 null and positive subjects.

The study cohort will be monitored through genetic screening to ensure that individuals with GSTM1 null genotype are represented in a proportion approximately equal to the prevalence in the US population, about 40%.

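### Single-genotype enrolment periods are not tied to season and the stated ANOVA leaves out measured CAP mass, so the null-versus-sufficient contrast has a small, cheaply closed exposure to dose imbalance

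*Protocol*

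**What the plan says.** **Aim.** A.4.1: "This study will compare responses to PM exposure in older volunteers with GSTM1 null and sufficient genotypes". A.4.8 sets the total at about 30 subjects so that this difference can be examined.

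**Dose.** A.4.5 (CAP Exposures): "The concentration of particles delivered to the chamber will vary depending on the levels of naturally occurring particles in the Chapel Hill air". Ambient peaks are given as 50-60 ug/m3 in summer and lower otherwise, and delivered mass as up to 600 ug/m3. Three features narrow the spread:
- the mask: "A face mask is used to reduce the daily and seasonal variability of PM concentration";
- dilution, which starts at about 500 ug/m3 (Protocol Operations Plan, 2.0 Task 1);
- rescheduling: "The CAP exposure day may be rescheduled if the particulate concentrations are too low on the scheduled day". The Operations Plan makes this the investigator's decision when the estimate is below 50 ug/m3.

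**Enrolment.** A.4.5 (Screening): "Depending on the need to maintain a representative population of subjects over time, GSTM1 null or sufficient subjects may be enrolled exclusively". The timing of such periods is left open. A.4.8 adds that the cohort is monitored so that "individuals with GSTM1 null genotype are represented in a proportion approximately equal to the prevalence in the US population", about 40%. B.3 expects a study of about 18 months.

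**Measurement and analysis.** Filters from the CAP sessions are "analyzed for both mass and chemical composition of particles", and the Operations Plan (3.0 Task 2) provides a spreadsheet of mass concentrations. The stated analysis is "Statistical data analyses will consist of ANOVA for continuous variables and rank sum tests for non-continuous variables pre- and post-exposure". It names no dose term.

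**The concern.** Genotype is compared between subjects, and each subject contributes one CAP dose. The clean-air session removes subject background from the CAP-minus-air response. It does not remove differences in CAP mass from one subject to another.

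A rule that lets one genotype be enrolled alone for a time, combined with a dose that changes with season, could give the two genotypes different mean doses. If response rises with mass, the stated ANOVA would count that difference as a genotype effect. Ordinary chance imbalance is already covered by the 5% level. A block of one genotype exposed in one season is not, because its members share that season's dose. Only the overall null share is controlled, not when each genotype is exposed.

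What is at stake is the null-versus-sufficient comparison. The within-subject CAP-versus-air contrast is unaffected.

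**Working it through.** **1. The plan's own figure.** A.4.8: difference 10%, SD 9%, power 0.8, alpha 0.05, N = 15. Sidedness is not stated; two-sided is assumed.
- Two-sample normal approximation: 13 per group.
- Two-sample t: 13.7, so 14 per group.
- Paired t with SD of differences 9 × √2: 14.75, so 15.

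The figure reproduces closely enough, so sample size is not at issue. With 40% of 30 null, the split is 12 versus 18, and t-test power for a difference of 10 is 0.82.

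**2. Assumptions that the documents do not supply.**
- No true genotype effect.
- CAP-minus-air response proportional to mass, equal to 10 points at the overall mean dose in both genotypes (full slope) or 5 points (half slope).
- Residual SD 9.
- One third of sessions outside an exclusive block fall in summer.
- Summer delivered mass is k = 1.5 or 2 times the rest of the year.
- An exclusive null block of m = 3 or 6 of the 12 null subjects is exposed wholly in summer.

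**3. Mean-dose ratio from a block.** The share of null sessions in summer is pn = (m + (12 − m)/3)/12, which is 0.50 for m = 3 and 0.667 for m = 6. The null:sufficient ratio is r = (1 + (k − 1) × pn) / (1 + (k − 1)/3). For k = 2 and m = 6: 1.667/1.333 = 1.25.

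**4. Bias and false positives without the mass term.** Bias at full slope = 10 × (r − 1) × 30/(18 + 12r), because the overall mean dose is (18 + 12r)/30 in units of the sufficient mean. At r = 1.25 this is 75/33 = 2.27 points. The standard error of the contrast is 9 × √(1/12 + 1/18) = 3.354. The false-positive rate follows from the noncentral t distribution with 28 degrees of freedom and noncentrality bias/3.354.

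| k | m | r | Bias, full slope | False positives, full slope | Half slope |
|---|---|---|---|---|---|
| 1.5 | 3 | 1.07 | 0.69 | 5.5% | 5.1% |
| 2 | 3 | 1.125 | 1.19 | 6.4% | 5.3% |
| 1.5 | 6 | 1.14 | 1.35 | 6.8% | 5.4% |
| 2 | 6 | 1.25 | 2.27 | 10.0% | 6.2% |

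Simulation that adds dose scatter within each genotype (uniform ranges 100-300, 50-600 and 30-400 ug/m3) gives 9.0-9.7% at r = 1.25 with full slope and 6.2-6.3% with half slope. With a flat dose-response the rate is about 5% at every ratio.

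**5. With centred mass in the model.** Simulated false-positive rates are 4.8-5.3% throughout.

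**6. Cost in power** (true difference 10).
- Flat dose-response, balanced doses: 0.82 without the term, 0.80-0.81 with it.
- Adjusted power at r = 1.25: 0.75-0.78.
- Adjusted power at r = 1.5: 0.63-0.74.

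The loss grows as genotype and dose align. Spreading exposure dates is therefore the better protection, with the covariate as support.

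**The case against.** **The SAP may already adjust.** A.4.8 names families of tests, not covariates, and covariates are commonly left to the SAP, which is not at hand. The mass data are collected and nothing bars their use. This stands, so the analysis half is conditional. The enrolment rule belongs to the Protocol, and adjustment works less well once genotype and dose overlap little.

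**The enrolment rule has a protective aim.** It is a permission, to be used to keep the population representative over time. Enrolment also precedes exposure by about six weeks of diet restriction, and CAP days can be moved. An enrolment block need not become an exposure block in the same season. This also stands. The rule lessens the risk, but nothing in it refers to season or to exposure dates.

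**The seasonal dose ratio is assumed.** The Protocol gives ambient summer peaks, not seasonal means of delivered mass, and the mask, dilution and rescheduling narrow the range. This is correct. These features reduce the spread, but no mechanism equalises dose between about 50 and 500 ug/m3.

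**Both genotypes must respond.** If only null subjects respond to CAP, a dose imbalance rescales a real effect and creates no false positive. This is also true.

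**A stronger reading to avoid.** A reader might infer that the genotype comparison is confounded as designed, or that false positives near 20% are to be expected. Simulated rates of 19-21% need a mean-dose ratio of 1.5, for example 80% of null but 20% of sufficient sessions in summer at double mass (1.8/1.2 = 1.5). The documents point to no such alignment.

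**Conclusion.** The concern holds as a minor point. The Protocol permits single-genotype enrolment periods without regard to season, dose varies with season, and the stated analysis leaves out a dose measure that the study already obtains. Bias in the genotype contrast needs three things together: clustering of one genotype's CAP sessions, a real seasonal difference in delivered mass, and a dose-response in both genotypes. None of these is documented.

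Under the assumed blocks, bias is about 0.7 to 2.3 points at full slope, against the 10% difference used for sample size. The increase in false positives is small and, at half slope, close to nil. The Protocol should not be read as predicting an imbalance. The case for a change rests on its low cost and on being able to tell a positive genotype result from a dose difference.

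**What to change.** 1. **A.4.5, Screening.** Add: When one genotype is enrolled exclusively, CAP exposure dates of both genotypes will be kept spread across seasons as far as practicable.
2. **A.4.8, continuous endpoints.** Unless the SAP already does so, include each subject's centred filter-weighed CAP mass as a covariate in the genotype comparison of the CAP-minus-air response, and report mean mass by genotype.

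**Cost.** The covariate uses one degree of freedom and data already collected; the power figures are in step 6 of the working. Recruitment may slow slightly. A mass term gives no protection against seasonal differences in particle composition or number, which is a further reason to spread the dates.

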## Part A.5. The Consent Process and Consent Documentation (including Waivers)

The standard consent process is for all subjects to sign a document containing all the elements of informed consent, as specified in the federal regulations. Some or all of the elements of consent, including signatures, may be altered or waived under certain circumstances.

- If you will obtain consent in any manner, complete **section A.5.1**.
- If you are obtaining consent, but requesting a waiver of the requirement for a signed consent document, complete **section A.5.2**.
- If you are requesting a waiver of any or all of the elements of consent, complete **section A.5.3**.
- If you need to access Protected Health Information (PHI) to identify potential subjects who will then be contacted, you will need a *limited waiver of HIPAA authorization*. This is addressed in section B.2.

You may need to complete more than one section. For example, if you are conducting a phone survey with verbal consent, complete sections A.5.1, A.5.2, and possibly A.5.3.

**A.5.1. Describe the process of obtaining informed consent from subjects.** If children will be enrolled as subjects, describe the provisions for obtaining parental permission and assent of the child. If decisionally impaired adults are to be enrolled, describe the provision for obtaining surrogate consent from a legally authorized representative (LAR). If non-English speaking people will be enrolled, explain how consent in the native language will be obtained. Address both written translation of the consent and the availability of oral interpretation. *After you have completed this part A.5.1, if you are not requesting a waiver of any type, you are done with Part A.5.; proceed to Part B.*

The subject will be given an opportunity to read the consent. At that time a member of the study team (usually the PI) will verbally describe the study and the subject will have an opportunity to ask questions or address concerns about any aspect of the study. The subject will be given a copy of the signed consent form for his/her records. Genotyping and consent forms will be administered by nursing staff and/or study team members. The Main Consent Form will be provided to the subject at the time of the Genotyping Screen visit.

**A.5.2. Justification for a waiver of written (i.e., signed) consent.** *The default is for subjects to sign a written document that contains all the elements of informed consent.* Under limited circumstances, the requirement for a signed consent form may be waived by the IRB if either of the following is true. *Chose only one:*

a. The only record linking the subject and the research would be the consent document and the principal risk would be potential harm resulting from a breach of confidentiality (e.g., study topic is sensitive so that public knowledge of participation could be damaging). \_\_ yes \_\_ no

**Explain.**

b. The research presents no more than minimal risk of harm to subjects and involves no procedures for which written consent is normally required outside of the research context (e.g., phone survey). \_\_ yes \_\_ no

**Explain.**

*If you checked "yes" to either (and you are not requesting a waiver in section*

*A.5.3) consent must be obtained orally, by delivering a fact sheet, through an online consent form, or be incorporated into the survey itself. Include a copy of the consent script, fact sheet, online consent form, or incorporated document.*

- If you have justified a waiver of written (signed) consent (A.5.2), you should complete A.5.3 *only* if your consent process will not include all the other [elements of consent](#).

**A.5.3. Justification for a full or partial waiver of consent.** *The default is for subjects to give informed consent.* A waiver might be requested for research involving only existing data or human biological specimens (see also Part C). More rarely, it might be requested when the research design requires withholding some study details at the outset (e.g., behavioral research involving deception). In limited circumstances, parental permission may be waived. This section should also be completed for a waiver of HIPAA authorization if research involves Protected Health Information (PHI) subject to HIPAA regulation, such as patient records.

Requesting **waiver of some elements** (specify; see SOP 28 on the IRB web site):

Requesting **waiver of consent entirely**

If you check either of the boxes above, answer items a-f.. To justify a full waiver of the requirement for informed consent, you must be able to answer “yes” (or “not applicable” for question c) to items a-f. **Insert brief explanations that support your answers.**

a. Will the research involve no greater than minimal risk to subjects or to their privacy?  yes  no

